5.0 PRE-STUDY REQUIREMENTS

Pre-study requirements include:

- Administration of the screening consent and HIPAA authorization form;
- Eligibility screening by a study medical provider, including a skin examination and a review of the subject's medical history, concomitant medications, and supplements;

- Subjects must have mild (N=12), moderate (N=12), or severe (N=12) sun damage [1] of the skin on the forearms (Appendix C).

6.0 TREATMENT PLAN

6.1 Subject Recruitment

Thirty-six subjects will be recruited, anticipating that 80% will be fully eligible and will complete the study. Clinic staff will be responsible for study participant recruitment. Male and female individuals will be recruited through the dermatology clinic at the University of Arizona Cancer Center, advertisements, community outreach programs, and from previous study participants who have agreed to be contacted. Subjects will be screened by a medical provider to verify eligibility before enrollment.

6.2 Trial Schema

Informed consent will be administered to all study participants. Female participants of childbearing potential will undergo a urine pregnancy test prior to SSL exposures. If there is a scheduling issue, a pregnancy test will be repeated if ≥ 7 days elapse between MED determination and the administration of SSL at 2X MED for biopsy. Each study participant will act as his/her own control. Areas to be used for baseline biopsies, MED (minimal erythema dose) determination, and study biopsy sites will be marked on the participant's skin with non-permanent surgical marking ink.

MED will be determined on the left buttock. After the MED of the subject is determined, three biopsy sites will be outlined on the left forearm. Then SSL at a dose of 2X MED will then be administered at two of the biopsy sites on the left forearm. Skin punch biopsies will then be collected at 1 hour (± 15 minutes) and 24 hours (± 2 hours) post-SSL exposure. In addition, one 6mm skin punch biopsy sample will be collected from the left forearm at baseline to serve as an unexposed (SSL) control sample. The control sample will be collected from a site that is at least 6 cm away from the sites exposed to SSL. All of the biopsy samples will be collected as close to the exact target time as possible. Photographs will be taken of the left forearm prior to skin punch biopsies. Study participants will return for suture removal and follow-up from 10 to 16 days after the final biopsies are collected, and they will be followed for as long as necessary if complications occur. Study participants may have their sutures removed by an outside provider per their preference.

Table 1 Outline of Trial Schema (n = 36)

Screening	Informed Consent Form and HIPAA authorization form administered; Skin examination and medical history reviewed by study provider
Visit 1*	Urine pregnancy test if necessary; SSL exposures administered for MED determination to left buttock.
Visit 2	MED visually determined
Visit 3*	Photograph of left forearm will be taken; SSL to 2 biopsy sites on left forearm at a dose of 2X MED; Biopsy collected from control biopsy site (no SSL) on left forearm; Biopsy collected from 1-hour test site on left forearm.
Visit 4	Photograph of left forearm will be taken; Skin biopsy collected from left forearm at 24 hours after SSL exposure
Visit 5**	Sutures removed 10-16 days after Visit 3

* When possible, Screening Visit may be combined with Visit 1, and Visit 2 may be combined with Visit 3.

**Participant may have their sutures removed by an outside provider.

6.3 Determination of MED (Minimal Erythema Dose)

The MED of each subject will be determined using a solar simulator (Solar Light Co.). MED is defined as the smallest dose of energy necessary to produce confluent erythema with four distinct borders at 22-26 hours post-exposure.

6.3.1 Light Source

A solar simulator will be used. The emission spectrum is from 290 to 390 nm, with <1% energy contributed by wavelengths <290 nm.

6.3.2 Test Site Area

MED will be determined on the left buttock. The test areas will be delineated with a template and skin marker.

6.3.3 Test Sub-sites

Each test area will be subdivided into 6 sub-sites (each 1 cm²) corresponding to the LLG pattern on the solar simulator.

6.3.4 SSL Irradiation for MED Determination

The solar simulator will be accurately calibrated prior to each use. A series of 6 increasing SSL radiation exposures (expressed as mJ/cm²) will be administered to the sub-sites on each subject, with LLG 1 emitting the lowest dose of SSL and

LLG 6 emitting the highest dose. All immediate responses to exposure will be recorded. Following exposure, the test sites will be occluded until evaluation.

6.3.5 Determination of MED

After 22 - 26 hours the test sites will be evaluated for the site and dose producing the MED as defined above.

6.3.6 Evaluation of Test Sites

Evaluation will take place under the same conditions (lighting and position) used when the test sites were irradiated.

7.0 BIOPSY SAMPLE COLLECTION, PROCESSING AND ANALYSES

7.1 Biopsy Procedure

One 6mm skin punch biopsy from the left forearm will be obtained at baseline, at a site at least 6 cm away from SSL exposure, to serve as a control sample (unexposed to SSL). In addition, one 6mm skin punch biopsy sample will be obtained from each biopsy site exposed to a single dose of SSL given at 2X the subject's MED.

Skin will be disinfected with an alcohol preparation, a 30-gauge needle will be used to inject lidocaine 2% with epinephrine, and punch biopsies (6mm in diameter and 0.8mm in depth) followed by suture closure will be obtained for RPPA and IHC analyses.

Table 2. Biopsy samples to be collected.

Bx	Test Site	Collection Timepoint	Initial Processing in Clinic	Analysis
1	Left forearm	control, 0 SSL	½ formalin + ½ snap frozen	Histology/IHC/RPPA
2	Left forearm	1° post 2xMED of SSL	½ formalin + ½ snap frozen	Histology/IHC/RPPA
3	Left forearm	24° post 2xMED of SSL	½ formalin + ½ snap frozen	Histology/IHC/RPPA

7.2 Formalin Fixation and Tissue Preparation

Each 6mm skin biopsy will be bisected immediately, with ½ snap frozen and the other ½ placed into 10% formalin. Fixation times have been standardized to 24 hr in formalin. After 24 hrs samples in formalin will be transferred to 70% ethanol until processing. Processing and paraffin embedding will be done weekly or bi-weekly so that no samples remain unprocessed for more than a week. Additionally, processing times and temperatures have been standardized and a tissue control is processed identically to samples with each run. Once skin samples are paraffin-embedded and mounted in blocks they are stored until they are batched for analyses.

7.3 Immunohistochemistry (IHC) Assays

Tissue sections at 3-5 microns will be cut, followed by deparaffinization and rehydration. All tissue sections will be subjected to antigen retrieval using a citrate buffer in a Decloaking Chamber Pro (Biocare, Walnut Creek, CA). Immunohistochemical staining will be performed using a Universal Alkaline Phosphatase RED biotin-free, multimer-based detection system or a streptavidin-biotin peroxidase system with a DAB chromagen and a hematoxylin counterstain (Ventana Medical Systems, Tucson, AZ) on an automated BenchMark® XT immunostainer (Ventana Medical Systems, Tucson, AZ) or by hand using an appropriate VECTASTAIN ABC Kit (Vector Laboratories, Burlingame, CA) depending on the primary antibody species and an alkaline phosphatase substrate for detection. In the case where mouse tissue will be stained with mouse primary antibodies, the Mouse on Mouse (M.O.M.™ Vector Laboratories, Burlingame, CA) will be used. Positive controls will be included in each IHC assay and negative controls will include the omission of the primary antibody with replacement by a normal serum from the same species as primary antibody. Biopsies will be batched for all analyses.

Tissue sections will be measured using ImagePro Plus (Media Cybernetics, [name]) software systems and a Leica DMR microscope (Westzlar, Germany), and a Sony 3CCD color video camera (Japan). The percent positive nuclear or cytoplasmic area per 40X field will be determined for each biopsy. A positive control slide for each IHC assay will be included when samples undergo image analysis to assess the daily variability of image analysis. Ten percent of samples will be repeated to assure assay reproducibility in a blinded manner as determined by the Biometry Core.

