1.0 OBJECTIVES

The overall goal of the Skin Cancer Prevention Program Project is to employ novel technologies and develop new therapeutic strategies to prevent intraepithelial neoplasias in the skin (i.e. actinic keratosis, cutaneous squamous cell carcinoma *in situ*). Our objectives in pursuit of this goal are to determine clinical, histopathologic, and protein/phosphoprotein signaling patterns associated with human skin carcinogenesis and to develop safe, highly efficacious intervention strategies for the prevention of skin cancer. The **overall hypothesis of the project** is that Toll-like Receptor 4 (TLR4) and T-LAK cell-originated protein kinase (TOPK) / p53-related protein kinase (PRPK) drive important signaling pathways, with potential synergism to prevent cutaneous squamous cell carcinoma (cSCC), and that TOPK/PRPK and TLR4 signaling pathways are modulated in the skin by acute exposure to solar simulated light (SSL).

The aim of this study is to assess TLR4 and TOPK/PRPK signaling in sun damaged (SD) human skin acutely exposed to solar simulated light (SSL). The purpose of this aim is to assess the effect of acute UV exposure on the signaling pathways of interest in order to validate the acute clinical model prior to intervention with small molecule inhibitors. Acute UV exposure will be evaluated in SD skin to determine the level of activation of the targeted pathways using reverse-phase protein array (LCM-RPPA) analysis and immunohistochemistry (IHC). This translational aim will prospectively analyze TLR4 and TOPK/PRPK signaling pathways activation by acute exposure of human subjects to SSL at twice the minimal erythema dose (MED) for each subject. We will evaluate the modulation of key proposed signaling pathways using RPPA and IHC in acutely irradiated human skin. We will also determine the optimal time points for evaluation of biomarker modulation.

Primary Endpoint: To assess TLR4 and TOPK signaling pathway activation levels pre- and post-SSL exposure in SD skin.

Exploratory Endpoint: To assess the correlation between SD level and the magnitude of SSL-induced pathway activation.

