8.0 STATISTICAL CONSIDERATIONS

8.1 Sample Size Determination

We will examine the TLR4 and TOPK signaling pathways in acute SSL-exposed SD human skin. Subjects with evidence of SD will be enrolled (N=36); with 85% expected to complete the study (30 evaluable subjects). Primary analysis will compare levels of RPPA analytes in each pathway as stated above in baseline unexposed samples vs. samples collected 1 or 24 h after SSL in SD skin. The power is 93% or above when the correlation between the \log_2 fold change of any two different analytes in the same pathway ranges from 0 to 0.4, and the power is 82% if the correlation is 0.6. Exploratory analyses will associate the SD score/severity level with analyte activation in the SD samples. Based on these analyses, the most appropriate post-SSL time point (per pathway) will be selected based on the combination with the largest effect sizes. Furthermore, an exploratory systems biology analysis will be conducted based on these analyses, one post-SSL time point (per pathway) will be selected for future studies based on the combination with the largest effect sizes. Furthermore, an exploratory systems biology analysis will be conducted.

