9.0 EARLY STOPPING

9.1 Early Stopping for Futility

Accrual will be halted after five participants have completed SSL exposure. Samples will be evaluated for changes in at least two biomarkers. If no changes are observed in any of the participants, other biomarkers will also be assessed. If no changes in any of the biomarkers are observed in any of the participants in a given group, accrual will stop

and the protocol will be re-evaluated to determine if the SSL doses should be adjusted or the trial should be stopped. Assuming that the response rate for any marker is as low as 50%, there is only a one in 32 (i.e., approximately 0.03) probability of seeing five non-responders, based on the binomial distribution, in a particular marker. The prospect of failing to see response in any of the markers, assuming that two or more are actually valid, is vanishingly small. Thus, choosing a sample size of five for initial assessment runs very little risk of committing a false negative error. This initial process will not assess success, and no inferential statistical analyses will be conducted. Only the presence or absence of expression will be noted.

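### Section 7.3 specifies blinding only for the 10% repeat IHC samples; the main IHC reads are not stated to be masked to exposure or time point

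*Combined protocol and SAP*

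**What the plan says.** Section 7.3 describes the IHC read in two steps. The instrument is named first: "Tissue sections will be measured using ImagePro Plus", with a microscope and a video camera. The outcome follows: "The percent positive nuclear or cytoplasmic area per 40X field will be determined for each biopsy". Quality measures are positive and negative controls, a positive control slide at image analysis, and batching ("Biopsies will be batched for all analyses").

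Blinding appears once, attached to the repeat samples: "Ten percent of samples will be repeated to assure assay reproducibility in a blinded manner as determined by the Biometry Core". Sections 7.1, 7.2, 7.4, 8.1 and 9.1 add nothing on masking.

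On the comparison, Section 6.2 states: "Each study participant will act as his/her own control". On the role of IHC, Section 1.0 states: "We will evaluate the modulation of key proposed signaling pathways using RPPA and IHC in acutely irradiated human skin". Section 2.2 lists nine IHC markers and adds previously established assays to validate the SSL-induced changes. Section 8.1 places the primary inference elsewhere: "Primary analysis will compare levels of RPPA analytes in each pathway as stated above in baseline unexposed samples vs. samples collected 1 or 24 h". The five-participant look in Section 9.1 does not name its assay and says: "Only the presence or absence of expression will be noted".

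**The concern.** Percent positive area is computed by software, but the result depends on which fields are imaged and where the stain threshold is set. The plan does not say who makes those choices, by what rule, or with what knowledge of the slide's origin.

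The expected direction is known in advance. Section 2.2 reports that this group had already seen pTOPK and pPRPK rise from 5 min and stay raised to 24 h in sun-protected skin, with TLR4 pathway activation mainly at 24 h. Each subject contributes one unexposed and two exposed biopsies, so knowledge of slide identity bears directly on the paired contrast.

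At stake is the independence of the IHC results as corroboration of RPPA. The study is meant to validate an acute exposure model before inhibitor studies (Sections 1.0 and 3.0 aside, this purpose is set out in the Objectives). If the supporting assay can drift toward the expected answer, agreement between the two platforms means less.

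**Working it through.** The plan gives no figure for masking or read bias, so there is none to reproduce. The check has four parts.

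**1. What the blinded repeats cover.** Inputs: 36 subjects (Section 8.1) and three biopsies each (Table 2).
- Planned biopsies: 36 × 3 = 108; 10% is 10.8, about 11.
- With the 30 evaluable subjects of Section 8.1 (36 × 0.85 = 30.6): 30 × 3 = 90; 10% is 9.

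About 90% of biopsies therefore have no blinded read specified. The repeats measure whether a reading can be reproduced; they do not remove bias from the main readings.

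**2. What the other safeguards do.**

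| Safeguard in 7.3 | What it addresses | Masks the reader? |
|---|---|---|
| Positive and negative controls | Staining validity | No |
| Control slide at image analysis | Day-to-day variability | No |
| Batching | Assay drift | No |
| Image software | Computation of area | Not by itself; field and threshold rules are not stated |
| Blinded 10% repeats | Reproducibility | Only for those repeats |

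**3. Illustration of size.** The documents give no IHC test, alpha or sidedness. Assume a two-sided 5% paired t-test on one marker with n = 30, no true effect, and a constant read bias of b standard deviations of the paired difference. The test statistic then follows a noncentral t distribution with 29 degrees of freedom and noncentrality b × √30, where √30 = 5.477. The false-positive rate is the probability that |t| exceeds the 5% critical value.

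| Assumed b | Noncentrality | False-positive rate |
|---|---|---|
| 0 | 0 | 5.0% |
| 0.1 | 0.548 | 8.3% |
| 0.2 | 1.095 | 18.5% |
| 0.3 | 1.643 | 35.5% |

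Nothing in the documents fixes b. The table shows only that a modest systematic shift matters at this sample size.

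**4. Does the same shift reach the sun-damage comparison?** Let each subject's change be d and the read bias a constant c. The correlation of d + c with the sun-damage score equals the correlation of d with that score, and c cancels from any difference between severity groups. A uniform shift therefore leaves that comparison unchanged. Only a bias that varied with sun-damage level would affect it, and none has been shown.

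**The case against.** The strongest reply is that IHC is not the primary analysis. Section 8.1 tests RPPA analytes, ties the sun-damage association to analyte activation, and bases the choice of time point on those analyses; it contains no IHC hypothesis test. Section 7.4 also states no masking, but the RPPA read-out is calibrated, background-subtracted and normalised by software. This stands, and it limits the point to supporting evidence.

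Second, the documents are silent on masking of the main reads. A reader might infer that they will be unmasked, or that an operator freely picks fields and cut-offs. The text says neither, and unwritten laboratory practice may already include coded slides. What stands is that masking, field selection and thresholds are not specified.

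Third, Section 9.1 names no assay, excludes inferential analysis and does not assess success. Bias toward activation there would only make the stopping rule less likely to trigger. That is fair, and it makes the early look a secondary and conditional concern.

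Fourth, full masking until a final lock would not work at the early look, because judging change requires knowing which sample is the control. This is correct and shapes the remedy.

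**Conclusion.** The point holds as a gap in how the supporting IHC data are produced. Followed as written, the plan gives the main IHC reads no stated protection against a reader who knows which slide is post-SSL, and the existing controls do not supply it.

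The 8% to 36% range is illustrative. It rests on an assumed test, an assumed alpha, n = 30 and an assumed bias of 0.1 to 0.3 SD. A reader might take it as the error rate of this trial's primary result, or carry it over to the sun-damage comparison. The documents support neither: the primary analysis is on RPPA analytes, and a uniform shift does not alter associations with sun-damage level. The consequence is weaker corroboration from IHC and, if IHC is used at the five-participant look, a possible tilt toward continuing accrual. It is worth correcting before reading starts, since masking cannot be added afterwards without re-reading the slides.

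**What to change.** State in Section 7.3 that:
- the Biometry Core codes all IHC slides;
- fields and thresholds follow a pre-specified rule, and slides are read masked to time point and sun-damage level;
- codes are released only after the image data are locked;
- if IHC is used in the Section 9.1 look, the first five participants have their own interim lock and code release, so that change from control can be judged;
- the 10% blinded repeats remain as a reproducibility check.

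The change needs no added biopsies, participant procedures or sample size. The cost is labelling and tracking. At one slide per marker (an assumption) and the nine markers of Section 2.2, that is 108 × 9 = 972 slides, or 90 × 9 = 810 for 30 evaluable subjects, before any previously established assays. Masking may also be imperfect where skin at 24 h after irradiation looks visibly different.

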7.4 Mapping of Protein Signaling Networks

Reverse-Phase Protein Array Construction: RPPAs will be constructed generally as described previously (Section 2.3). Briefly, lysates will be loaded into 384-well plates and serially diluted in lysis buffer for a two-point dilution curve (neat and 1/4). The RPPA technology has been developed and optimized for performance as a fluorescent-based calibrated assay, generally identical in design and analysis to standard ELISA or standard clinical immunoassays. As a calibrated assay, each assay consists of:

- a. Experimental patient samples printed in triplicate two-spot dilutions (neat and 1:4)
- b. High, medium, and low controls printed in triplicate two-spot dilutions (neat and 1:4)
- c. A calibrator, consisting of a 6-10-point curve whereby the analyte of interest is decreasing in concentration in the background of a constant protein concentration.

Image Analysis: The current iteration of the RPPA uses a fluorometric image capture processing system (NovaRay, Alpha Innotech) for image acquisition. The system measures the sample's fluorescence intensity value, subtracts the background, normalizes the result to the total protein, and extrapolates the value to the non-parametrically fit calibration curve to generate a final intensity value. The median of the triplicate values will be reported. Sypro-stained slides will be analyzed with MicroVigene image analysis software, version 2.200 (Vigenetech, North Billerica, MA) and Microsoft Excel 2000 software. Images will be imported into Microvigene, which performed spot finding, local background subtraction, replicate averaging, and total protein normalization to produce a single value for each sample at each endpoint.

8.0 STATISTICAL CONSIDERATIONS

8.1 Sample Size Determination

We will examine the TLR4 and TOPK signaling pathways in acute SSL-exposed SD human skin. Subjects with evidence of SD will be enrolled (N=36); with 85% expected to complete the study (30 evaluable subjects). Primary analysis will compare levels of RPPA analytes in each pathway as stated above in baseline unexposed samples vs. samples collected 1 or 24 h after SSL in SD skin. The power is 93% or above when the correlation between the \log_2 fold change of any two different analytes in the same pathway ranges from 0 to 0.4, and the power is 82% if the correlation is 0.6. Exploratory analyses will associate the SD score/severity level with analyte activation in the SD samples. Based on these analyses, the most appropriate post-SSL time point (per pathway) will be selected based on the combination with the largest effect sizes. Furthermore, an exploratory systems biology analysis will be conducted based on these analyses, one post-SSL time point (per pathway) will be selected for future studies based on the combination with the largest effect sizes. Furthermore, an exploratory systems biology analysis will be conducted.

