Thirty-six (36) subjects with a broad range of SD on the forearm will be recruited. Based on the standardized clinical photodamage scale [1], we will include mild (N=12), moderate (N=12), and severely (N=12) sun damaged (SD) skin. The level of SD will be scored, using a range of 0-9, where absent SD = 0, mild SD = 1-3, moderate SD = 4-6 and severe SD = 7-9 (see Appendix C).

We will irradiate and biopsy the SD forearm skin of each healthy adult volunteer and collect skin punch biopsies before and after exposure to SSL for analysis using LCM-RPPA and IHC. The results of this study will be used to aid in design of pharmacodynamic SSL exposure studies with small molecule inhibitors in subsequent studies.

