2.2 Immunohistochemistry

The use of immunohistochemical biomarkers permits studies with smaller sample size and shorter duration compared to studies that use cancer incidence as an endpoint. To be valid, the quantitative degree and pattern of biomarkers should correlate with carcinogenic transformation or alternatively biomarkers markers may demonstrate the effect of a particular agent on a molecular pathway or biochemical processes (i.e. arachadonic acid/cyclooxygenase pathways, polyamine synthesis). This has been demonstrated by the suppression of polyamine levels in tissue treated with the polyamine synthesis inhibitor, alpha-2-(Difluoromethyl)-dl-ornithine, or DFMO [20,21].

In a previous study completed by this group, IHC was performed on samples collected at baseline, 5 min, and 1, 5, and 24 h following 2X MED of SSL on SP skin of 10 subjects; there was a significant increase in pTOPK and pPRPK activity starting as early as 5 min post SSL exposure with a sustained expression up to 24 h (**Fig. 1**). Analysis of TLR4 using the same samples also revealed increased pathway activation primarily at 24 h post-SLL exposure.

IHC assays will include pTLR4, MyD88, p-p65/NFKB, TAB2, pTOPK, p-PRPK, p-Erk, pP38, and pP90RSK. IHC assays previously established will also be performed for validation of SSL-induced changes.

[figure not shown]

Fig. 1. Comparison of p-PRPK and p-TOPK levels on sUV-exposed human skin harvested in a time-dependent manner. IHC staining was performed and representative data analyzed (30 photos from 10 subjects) for each of the following: normal human skin without sUV, 5 min post 2X MED sUV, 1 h post 2 MED sUV, 5 h post 2 MED sUV and 24 h post 2 MED sUV. Shown is expression of phosphorylated (p)-PRPK (a) and p-TOPK (b). Magnification: 400x. **Upper panels:** Phosphorylated PRPK, total and p-TOPK levels are presented as sum of the integrated optical density (IOD) values. **Lower panels:** Representative staining (brown color) is shown. The asterisks (*, **) indicate a significant difference ($p < 0.05$ or $p < 0.001$, respectively).

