Activation of proteins by phosphorylation of kinase-driven signaling networks contains information regarding the disease process as well as potential therapeutic targets [23]. The phosphorylation state of proteins can be detected and assessed using specific phospho-specific antibodies developed to recognize the phosphorylated isoform of the kinase substrates [23-25]. Each antibody undergoes extensive validation for specificity prior to RPPA analysis using peptide competition and single band detection on Western as well as ligand induction. Currently, [name] has over 300 extensively validated different cell signaling antibodies in his portfolio. Using RPPA, many dozens of kinase substrates can be quantified and measured simultaneously through multiplexed phosphospecific antibody analyses. RPPA has demonstrated sensitivity, precision and accuracy that enable the evaluation of signaling networks from a very small number of cells (e.g. procured using laser capture microdissection) from biopsy material.

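### Does the missing test, alpha, effect size and RPPA analyte list behind the 93%/82% power in section 8.1 call for a change to the primary analysis?

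*Combined protocol and SAP*

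**What the plan says.** Section 1.0 sets the goal: "Primary Endpoint: To assess TLR4 and TOPK signaling pathway activation levels pre- and post-SSL exposure in SD skin". It adds that the results "will be used to aid in design of pharmacodynamic SSL exposure studies" with small-molecule inhibitors.

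Section 8.1 is the only account of the primary analysis: "Primary analysis will compare levels of RPPA analytes in each pathway as stated above in baseline unexposed samples vs. samples collected" 1 h or 24 h after SSL. It gives 36 enrolled, 85% completing and 30 evaluable. It states power by between-analyte correlation, with at least 93% at the low end. The sentence on this reads in part: "fold change of any two different analytes in the same pathway ranges from 0 to 0.4, and the power is 82" (a percentage, which applies at 0.6). On the time point to carry forward, it says that "one post-SSL time point (per pathway) will be selected for future studies based on the combination with the largest effect sizes".

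The back-reference in the primary-analysis sentence reaches no RPPA list. Section 2.2 has the only list of markers, and it is for the other assay: "IHC assays will include pTLR4, MyD88, p-p65/NFKB, TAB2, pTOPK, p-PRPK, p-Erk, pP38, and pP90RSK". Section 2.3 mentions "over 300 extensively validated different cell signaling antibodies", which is the laboratory's portfolio and not this trial's panel. Section 6.1 recruits 36 subjects, "anticipating that 80% will be fully eligible and will complete the study".

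**The concern.** An analysis labelled primary, with N justified by power, should let a reader see what was powered. Here the test, alpha, sidedness, effect size, SD, number of analytes and multiplicity rule are all absent. The only significance levels in the document (0.05 and 0.001) are in the Figure 1 legend and belong to earlier IHC data. Power that varies with between-analyte correlation implies a definite multi-analyte calculation, yet none is written down.

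Two things would be at stake. A reader cannot say what size of pathway activation 36 subjects were chosen to detect. Also, an analyte set and test settled after the RPPA results were seen would still comply with the text, and testing two times in two pathways without adjustment could raise the false-positive rate.

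**Working it through.** **Inputs.** From section 8.1: 36 enrolled, 85% completion, 30 evaluable, log2 fold change, 93% at correlation 0.4 and 82% at 0.6. From section 6.1: 80% completion. From section 6.2: each subject is his or her own control, so the comparison is paired. The test, alpha, number of analytes K, effect size and correlation between times are assumptions throughout.

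**1. Evaluable n.** 36 × 0.85 = 30.6, which reproduces the stated 30. At 80%, 36 × 0.80 = 28.8, so 28 or 29.

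**2. Can the stated power arise from an ordinary test?** Take a paired t-test on the mean of K analytes, with equal effects of d SD per analyte and a common correlation ρ. The standardized pathway effect is D = d / √((1 + (K − 1)ρ)/K), and the noncentrality is D√n.

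At n = 30 and two-sided 0.05, 93% power needs D = 0.649 and 82% needs D = 0.543, a ratio of 0.649/0.543 = 1.195. Moving ρ from 0.4 to 0.6 with K = 16 gives a ratio of √((1 + 15 × 0.6)/(1 + 15 × 0.4)) = √(10/7) = 1.195. The two published figures therefore agree with each other under this test, with d = 0.649 × √(7/16) = 0.43.

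**3. Is that the only fit?** No. Fixing 93% at ρ = 0.4 and n = 30:

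| Assumed test | K | Alpha | d (SD) | Power at ρ = 0.6 |
|---|---|---|---|---|
| Mean, paired t | 16 | 0.05 two-sided | 0.43 | 82.0% |
| Mean, paired t | 7 | 0.0125 two-sided | 0.53 | 82.1% |
| Mean, paired t | 5 | 0.05/18 = 0.0028 two-sided | 0.64 | 82.1% |
| Mean, paired t | 40 | 0.05 one-sided | 0.38 | 82.4% |
| Hotelling T² | 7 | 0.05 | 0.66 | 81.9% |
| Hotelling T² | 4 | 0.0028 | 0.82 | 82.1% |

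For Hotelling, the noncentrality is n·d²·K/(1 + (K − 1)ρ). All six round to 82%. They show that the inputs cannot be recovered. They do not bound the detectable effect, and none contradicts the stated power.

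**4. Effect of 80% completion.** Keeping D = 0.649 and 0.543 (two-sided 0.05 paired t): n = 29 gives 92.1%/80.6% and n = 28 gives 91.2%/79.1%.

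**5. Error rate and the two times.** Suppose each time were tested at two-sided 0.05, either time counted as success, and the times correlated 0.5. The false-positive rate would be 0.091 per pathway, and 1 − (1 − 0.0907)² = 0.173 across two independent pathways. The document says neither that this rule applies nor that it does not.

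Splitting alpha to 0.025 per time under the same rule, with the effects from step 2, simulation gives:

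- both times active: about 96%/87%, above the stated 93%/82%;
- only one time active: about 88%/74%.

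Even if the published power covered a single time at 0.05, handling both times strictly would not in general force a larger trial.

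**6. What does the written decision use?** Section 8.1 picks the time point by effect size, not by significance, so the rates in step 5 do not describe the risk of carrying forward the wrong time. The other written decision, the five-participant check in section 9.1, expressly involves no inferential analysis.

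**The case for a change.** The strongest case for a change is that the protocol chose to call this analysis primary, set it apart from exploratory work and justify N by power, and those choices carry a duty to state the inputs. The analyte set per pathway is open, including whether PRPK counts under TOPK. The effect-size measure used to choose the time point is undefined. The analysts could settle all of this after seeing data and still be within the text.

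The omissions stand. Nothing in section 8.1 looks redacted, and no other section supplies them. But the freedom is narrower than it seems. The comparison is within subject, on a log2 fold-change scale, confined to two named pathways and worded per pathway. The nine IHC markers in section 2.2 are a natural starting set. Copying the inputs of the existing calculation into the record may be all that is needed. Choosing among Holm, a joint two-time test or no adjustment is a trade-off between power and error control, and the documents do not show that any choice already made is wrong.

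**Conclusion.** The power statement is incomplete, but no change to the design or primary analysis follows. The 93%/82% figures are coherent with each other under a standard paired pathway-level test and are matched by several assumed specifications, so they are unverifiable without being shown wrong. No inflation of error is demonstrated. The 80%/85% mismatch is a clerical slip worth about 1 to 3 points of power, given a two-sided 0.05 paired t-test.

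The remaining gap is one of documentation: which analytes, which test, which alpha, how 1 h and 24 h are handled, and which effect-size measure. Analysts can fill it sensibly, provided that they do so before the RPPA results are analysed. This is a 36-volunteer, own-control study with no drug, whose output informs the design of later studies, so that is a proportionate reading.

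Two limits apply. The conclusion does not certify the power, and the least favourable split-alpha case in step 5 (one active time, stated power computed for a single time at 0.05) would bring it to about 88%/74%.
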